#### **11.5.3.4 Duration of Overall Response**

The duration of overall response is measured from the time measurement criteria are met for CR or PR (whichever status is recorded first) until the first date that recurrence or PD is objectively documented, taking as reference for PD the smallest measurements recorded since the treatment started.

#### **11.5.3.5 Duration of Stable Disease**

SD is measured from the start of the treatment until the criteria for disease progression are met, taking as reference the smallest measurements recorded since the treatment started. The clinical relevance of the duration of SD varies for different tumor types and grades. Therefore, it is highly recommended that the protocol specify the minimal time interval required between two measurements for determination of SD. This time interval should take into account the expected clinical benefit that such a status may bring to the population under study.

#### **11.5.3.6 Objective Response Rate**

ORR is defined as the percentage of patients that achieve PR or CR.

#### **11.5.3.7 Disease Control Rate (DCR)**

DCR is defined as the percentage of patients that achieve an objective tumor response or have stable disease to therapy.

#### **11.5.3.8 Progression-Free Survival (PFS)**

PFS is defined as the duration of time from date of enrollment to time of progression or death, whichever occurs first.

#### **11.5.3.9 Overall Survival (OS)**

OS is defined as the duration of time from date of enrollment to death from any cause.

#### **11.5.4 Reporting of Results**

All patients included in the study must be assessed for response to treatment, even if there are major protocol treatment deviations or if they are ineligible. Each patient will be assigned one of the following categories: 1) complete response, 2) partial response, 3) stable disease, 4) progressive disease, 5) early death from malignant disease, 6) early death from toxicity, 7) early death because of other cause, or 9) unknown (not assessable, insufficient data).

All of the patients who met the eligibility criteria should be included in the main analysis of the response rate. Patients in response categories 4-9 should be considered as failing to respond to treatment (disease progression). Thus, an incorrect treatment schedule or drug administration, or failure to complete all prescribed study therapy, does not result in exclusion from the analysis of the response rate. All conclusions should be based on all eligible patients. Sub analyses may then be performed on the basis of a subset of patients, excluding those for whom major protocol deviations have been identified (e.g., early death due to other reasons, early discontinuation of

treatment, major protocol violations, etc.). The reasons for excluding patients from the analysis should be clearly reported.

## 11.6 Safety

Safety assessments will consist of monitoring and recording all adverse events, including serious adverse events, the monitoring of hematology, blood chemistry, coagulation parameters, urinalysis and the regular monitoring of vital signs, and physical condition as shown in corresponding tables. For details on AE collection and reporting, refer to the Safety section in the protocol.

## 12.0 CORRELATIVES

One of the major shortcomings of immunotherapy trials has been the lack of in depth correlative studies to help identify the mechanism of action of these therapies, identify biomarkers of response, and provide a foundation for further improving these approaches. To address this we plan to perform in depth immunological analysis of patient blood and tumor samples. Pre- and post-treatment blood and tumor biopsies (when available) will be obtained as outlined in the study calendar. Briefly, blood and tumor samples will be collected as detailed in the study calendar. Optional blood and tumor biopsies can be obtained at progression. Participation in the correlative studies is mandatory unless waived by the study principal investigator due to safety concerns or other reasons. Archival tumor blocks will also be collected when available. We will evaluate immunologic changes systemically and in the tumor and tumor microenvironment within patient's pre to post therapy and across the cohort of patients to identify predictive biomarkers and elucidate the mechanistic immunologic effects of therapy. For further details, refer to Appendix 4. Correlative studies will include (in order of priority):

### 12.1 Blood

- FACS for quantification, immunophenotyping, and functional assessment of PBMCs
- Evaluation of immune related gene signatures by RNAseq and/or Nanostring
- Whole exome sequencing (as normal tissue baseline for determining mutational burden and neoantigen load of tumors)
- Ex Vivo evaluation of T cell function by in vitro stimulation studies and metabolic status by seahorse analysis
- Evaluation of systemic plasma tryptophan to kynurenine ratios
- Luminex evaluation of plasma for systemic cytokine / chemokine signatures
- T-cell receptor (TCR) deep sequencing to determine clonal expansion and diversity of T-cells in the systemic circulation
- Other studies as deemed feasible and informative by the principal investigator

## 12.2 Tissue

- Multi-plexed IHC/IF to determine expression of markers including PD-1, PD-L1, CD8, CD4, IDO1, Ki-67, Granzyme b and FOXP3
- Evaluation of immune related gene signatures by RNAseq and/or Nanostring
- T-cell receptor (TCR) deep sequencing to determine clonal expansion and diversity of T-cells in the tumor microenvironment
- Evaluating mutational burden and neoantigen load of tumors using RNAseq and WES data
- Flow cytometry and ex-vivo analysis of T-cells from fresh tumor biopsies
- Other studies as deemed feasible and informative by the principal investigator

## 12.3 Stool

- Stool microbiome analysis

A comprehensive analysis of tumor, blood, and stool samples will provide valuable insight into potential biomarkers and into the mechanism of action of our combined therapy.

Blood samples will be separated into PBMCs and plasma and stored at -80°C for batched analysis. PBMCs will be stained for FACS analysis using well characterized antibodies against markers such as CD45, CD3, CD4, CD8, FOXP3, Granzyme B, Interferon gamma, tumor necrosis factor (TNF) alpha, PD-1, PD-L1 etc. Results will be analyzed using a BD Fortessa multi-color flow cytometer and Flowjo software. An aliquot of PBMCs will also be set aside for RNA isolation and batched analysis of gene expression. An aliquot of PBMCs at baseline blood draw will also be set aside for DNA extraction for WES. To determine if certain clones of T cells are preferentially expanding after therapy, an aliquot of PBMCs will also be used for TCR deep sequencing. Plasma will be evaluated for systemic cytokine and chemokine signatures using Luminex technology. Markers will include IL-2, IL-6, IL-10, IL-12p70, GM-CSF (granulocyte-macrophage colony-stimulating factor), TNF alpha, IFN (interferon) gamma, CXCL10 (C-X-C motif chemokine 10), RANTES (regulated on activation, normal T cell expressed and secreted), MIP1 (Macrophage Inflammatory Protein) alpha, MIP1 beta, TGF-beta and others. Systemic tryptophan and kynurene levels will also be evaluated.

Tissue biopsies will be formalin fixed and paraffin embedded using standard protocols. Tissue will be analyzed by multi-plexed IHC/IF staining for markers including PD-1, PD-L1, CD8, CD4, IDO, Ki-67, Granzyme b and FOXP3. An aliquot of tumor tissue will be stored in RNA later for batched analysis of gene expression signatures and TCR deep sequencing. If sufficient tissue is available an aliquot will be freshly processed to evaluate T cell function and metabolic status. Pre-treatment stool samples will be collected to analyze the gut microbiome

## 13.0 DRUG INFORMATION

### 13.1 BMS-986205

#### 13.1.1 Dosing and Administration

BMS-986205 will be dispensed once every 28 days and administered at 50-100mg orally, daily throughout the study period. Subjects will take their dose of BMS-986205 once a day around the same time during the day. Subjects should take the tablet with 240 ml/8 ounces of water following a meal.

#### 13.1.2 Formulation, Packaging, and Handling

BMS-986205-04 Film-coated Tablet, 100 mg (30 tablets per bottle): BMS-986205-04 tablet is a light pink to pink, oval-shaped, plain-faced, film-coated tablet. In addition to BMS-986205-04 drug substance, the following formulation excipients are used: anhydrous lactose, microcrystalline cellulose, crospovidone, silicon dioxide, magnesium stearate, and Opadry® pink color dispersion. The tablets are supplied in tightly-closed high-density polyethylene bottles with child-resistant closures containing a desiccant.

BMS-986205-04 Film-coated Tablet, 50 mg (30 tablets per bottle): BMS-986205-04 tablet is a beige, oval-shaped, plain-faced, film-coated tablet. In addition to BMS-986205-04 drug substance, the following formulation excipients are used: anhydrous lactose, microcrystalline cellulose, crospovidone, silicon dioxide, magnesium stearate, and Opadry® beige color dispersion. The tablets are supplied in tightly-closed high-density polyethylene bottles with child-resistant closures containing a desiccant.

BMS-986205-04 tablets should be stored at 2°C to 30°C (36°F to 86°F) in a tightly-closed container protected from light.

For complete details on drug preparation, administration, storage conditions, clinical pharmacology, pharmacokinetics, and known precautions and adverse reactions please see the BMS-986205 IB.

#### 13.1.3 Preparation

No preparation is required for BMS-986205-04 capsules or tablets.

#### 13.1.4 Ordering / How Supplied

BMS-986205 will be supplied by BMS at no cost to study patients.

#### 13.1.5 Accountability, Handling and Disposal

Responsibility for drug accountability is on the investigator and the assigned pharmacist or designee. Drug supply will be disposed of according to institutional standard operating

procedure. Accurate records of all investigational product received at and dispensed from the study site should be recorded on the Drug Log.

## 13.2 Nivolumab

### 13.2.1 Dosing and Administration

Patients should be administered nivolumab 240 mg as an in intravenous infusion over 30 minutes every 2 weeks ( $\pm$  1 day for cycles 1 to 3 and  $\pm$  3 days for subsequent cycles). For the first infusion, the patient's vital signs (heart rate, respiratory rate, blood pressures, and temperature) should be determined within 60 minutes before, during (every 15 [ $\pm$ 5] minutes), and 30 ( $\pm$ 10) minutes after the infusion. For subsequent infusions, vital signs will be collected within 60 minutes before infusion. Patients will be informed about the possibility of delayed post-infusion symptoms and instructed to contact their study physician if they develop acute symptoms.

### 13.2.2 Formulation, Packaging, and Handling

Nivolumab will be supplied by Bristol-Myers Squibb and labeled appropriately as investigational material for this study. Nivolumab is a programmed death receptor-1 (PD-1) blocking antibody. Nivolumab vials must be stored in the refrigerator at 2-8°C, protected from light and freezing. If stored in a glass front refrigerator, vials should be stored in the carton. The product does not contain a preservative, and as such after preparation, nivolumab should be used immediately. If not used immediately, nivolumab infusions should be stored at room temperature (20-25°C) and room light for no more than 4 hours from time of preparation. This includes room temperature storage of infusion in IV container and time for administration of infusion. Alternatively, nivolumab infusion can be stored under refrigeration at 2 to 8°C (36-46°F) for no more than 24 hours from the time of infusion preparation and protected from light. The infusion should not be frozen.

Recommended safety measures for preparation and handling of nivolumab include laboratory coats and gloves.

For complete details on drug preparation, administration, storage conditions, clinical pharmacology, pharmacokinetics, and known precautions and adverse reactions please see the Nivolumab IB.

### 13.2.3 Preparation

Preparation of nivolumab should be performed by trained personnel in accordance with package insert and good practices rules, especially with respect to asepsis. The required volume of nivolumab should be withdrawn and transferred into an intravenous container. Nivolumab should be then be diluted with either 9 mg/mL (0.9%) sodium chloride solution for injection, USP or 50 mg/mL (5%) dextrose solution for injection, USP, to prepare an infusion with a final concentration ranging from 1 mg/mL to 10 mg/mL. Diluted solution should be mixed by gentle

inversion, but should not be shaken. Partially used or empty vials of nivolumab should be discarded.

#### **13.2.4 Ordering / How Supplied**

Nivolumab will be supplied by BMS at no cost to study patients.

#### **13.2.5 Accountability, Handling and Disposal**

Responsibility for drug accountability is on the investigator and the assigned pharmacist or designee. Drug supply will be disposed of according to institutional standard operating procedures. Accurate records of all investigational product received at and dispensed from the study site should be recorded on the Drug Log.

## 14.0 STATISTICAL CONSIDERATIONS

### 14.1 Study Design and Overview of Primary and Secondary Endpoints

This is a phase I/II study using a Simon optimal two-stage design for efficacy of BMS-986205 in combination with nivolumab. In the phase I portion, we will treat patients following 3+3 standard design with dose escalation in BMS-986205 along with fixed dose of nivolumab.

BMS-986205 dose level 1 will be 50mg and dose level 2 will be 100mg. 3 patients will be treated with BMS-986205 at dose level 1 of 50mg along with fixed dose of nivolumab. If no patient experiences a DLT at dose level 1, we will add 3 patients will be treated at a dose of 100 mg of BMS-986205 with fixed dose of nivolumab. If 1 of 3 patients has a DLT at DL1, we will add 3 patients at a dose of 50 mg. If  $\leq 1$  of 6 patients has a DLT at 50mg of BMS-986205, 3 patients will be treated at 100 mg. Maximum tolerated dose will be defined as  $\leq 1$  of 6 patients at DL1 or DL2 experiencing a DLT. After identifying the MTD, the phase II expansion phase will be initiated with 3 additional patients at the MTD. A maximum total of 17 patients at MTD will be treated on trial including 6 patients treated during phase I portion at MTD. An interim efficacy analysis will be done after 9 patients (including the 6 patients in phase I portion) have been treated. If at least 1 patient out of the 9 initial patients treated at MTD achieves a response, we will accrue 8 more patients at the MTD. If at least 3 of the 17 patients treated at MTD achieve a response, we will deem the treatment worthy of further study, provided the safety profile is acceptable.

### 14.2 Sample Size Estimation /Accrual Rate

The Simon optimal 2 stage design described above provides 80% power to detect the difference between an acceptable response rate by RECIST of 25% vs. an unacceptable rate of 5% at the 0.05 level (1-sided). The estimated time to accrue 23 patients is 24 months, at approximately 1 patient per month.

### 14.3 Evaluation of Efficacy

The ORR will be estimated as the proportion of participants who experience an objective response, along with its exact 95% confidence interval; the disease control rate will be analyzed similarly. DOR, PFS, and OS will be analyzed using Kaplan-Meier methods; medians and 95% confidence intervals will be computed.

### 14.4 Evaluation of Safety

DLTs, adverse events, serious adverse events, and clinical laboratory values outside normal limits will be listed for each patient and summarized by body system and dose level in frequency tables.

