In summary, BMS-986205 at 100 mg QD achieves trough plasma concentrations that exceed the human whole blood IC90, produces substantial serum kynureneine reductions similar to those observed at higher dose levels, demonstrates target engagement in the tumor microenvironment, appears (in combination with nivolumab) to have a more favorable tolerability profile compared to higher doses and overall similar to that of nivolumab monotherapy, and demonstrates clinical activity in combination with nivolumab[24]. Based on this evidence, BMS-986205 100 mg QD is the recommended phase 2 Dose (RP2D) in combination with nivolumab. For this study, we have chosen 50 mg QD as the starting dose level to be given with nivolumab 240mg to observe hepatotoxicity in an HCC population. BMS-986205 will be escalated to 100 mg QD with nivolumab when dose 1 level is shown to be tolerated.

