### 3.0 STUDY DESIGN

This is a phase I/II study using a Simon optimal two stage design for efficacy of BMS-986205 in combination with nivolumab as illustrated in the schema. For the phase I portion the primary endpoint is to determine safety profile of BMS-986205 in two dose levels with nivolumab in unresectable HCC using CTCAE V5.0 criteria. For the phase II portion the primary endpoints are safety and toxicity and the objective response rate using the using RECIST criteria. Exploratory endpoints include disease control rate (DCR), duration of response (DOR), ORR using iRECIST, progression free survival (PFS), overall survival (OS), and correlative studies.

For phase I dose escalation, up to two dose levels of BMS-986205 will be evaluated: 50 mg daily and 100mg daily. These two dose levels were selected based on the clinical data described above. We have chosen 50 mg daily as the starting dose level given the existing safety data for this dose and the safe use of this dose in use with other immunotherapy combinations. The dose of BMS-986205 will be escalated to 100 mg daily if 0 of the first 3 patients experience a dose limiting toxicity (DLT) at 50 mg BMS-986205. Three additional patients will be added to receive 50 mg BMS-986205 if 1 of the first 3 patients experiences a DLT. The dose of BMS-986205 will be escalated to 100 mg daily if no more than one of six patients experience a DLT at 50 mg BMS-986205. The expansion phase will be conducted after MTD is reached, which will be defined as no more than one of six patients develops a DLT at 50 mg or 100 mg of BMS-986205 daily with nivolumab. If BMS-986205 50mg daily is not tolerated the study will be halted and modified after discussion with the principal investigator (PI) and BMS. The 6 patients at the maximum tolerated dose in the phase I portion treated at MTD will count towards the 17 patients needed in the phase II expansion cohort. The phase II cohort will be run as a Simon two-stage design to allow for early trial stoppage for futility. We designate an ORR as defined by RECIST criteria of 5% as not worthy of further investigation and of 25% as worthy of further investigation. In the first stage 9 patients will be accrued and at least 1 response must be observed within 6 months of treatment (or longer at PI discretion) to continue the trial (n1=9, r1=0) (see study schema). BMS-986205 will be administered orally daily and nivolumab will be administered intravenously until disease progression.

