## 4.0 SUBJECT SELECTION

### 4.1 Inclusion Criteria

Patients must meet all of the following criteria to be eligible for study entry.

1. Men and women  $\geq 18$  years of age at the time of study entry.
2. Willing and able to provide written informed consent for the trial.
3. Life expectancy  $>12$  weeks.
4. Histologically or imaging confirmed hepatocellular carcinoma (mixed hepatocellular/cholangiocarcinoma or fibrolamellar subtypes are excluded).
5. Have disease that is not amenable for curative treatment approach.
6. Have measurable disease based on RECIST v1.1.
7.  $\geq 1$  liver lesions accessible for core biopsy that was either not previously treated by liver-directed therapy or progressed following liver-directed therapy.
8. Child-Pugh score of A.
9. ECOG performance status of 0 or 1.
10. Adequate hematology parameters:
  - a. Absolute neutrophil count (ANC)  $\geq 1000$  cell/mm $^3$
  - b. Platelet count  $\geq 50,000$ /mm $^3$
  - c. Hemoglobin (Hgb)  $\geq 8$  g/dL
11. Acceptable blood chemistry levels:
  - a. AST/SGOT, ALT/SGPT  $\leq 5$  x upper limit of normal (ULN)
  - b. Total bilirubin  $\leq 2$  ULN
  - c. Creatinine  $\leq 2$  x ULN
12. Subjects with active hepatitis B virus (Hep B) are allowed if antiviral therapy for hepatitis B has been given for  $>8$  weeks and viral load is  $<100$  IU/ml prior to first dose of trial treatment. Subjects with untreated hepatitis C virus (HCV) are allowed.
13. Willingness to undergo mandatory pre-treatment biopsy (unless there is adequate archival tumor specimen available) and mandatory on-treatment biopsy.

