### **5.5.3 Protocol-Specific Recommendation for Management of Hepatic Events**

Subjects with advanced HCC generally have underlying cirrhosis with decreased hepatic function. They may also have a concomitant chronic viral infection. For this study, the upper limits for inclusion were therefore adjusted to account for baseline liver dysfunction. Subjects with AST or ALT elevations within the CTCAE Grade 2 range are allowed to enroll in the study. This requires a protocol-specific approach for the management of hepatic events outlined as follows:

- Both BMS-986205 and nivolumab should be delayed for
  - Grade  $\geq 2$  toxicity in subjects with baseline AST or ALT within normal limit,
  - Grade  $\geq 3$  toxicity in subjects with baseline AST or ALT within grade 1 toxicity range
  - Drug related increase in AST or ALT at 2x baseline value or when AST or ALT is 8x ULN (whichever is lower) in subjects with baseline AST or ALT in grade 2 toxicity range.
- If AST or ALT levels do not improve with a dose delay of 3 - 5 days or if the levels worsen, initiate steroid therapy at 0.5 - 2 mg/kg/day methylprednisolone or oral equivalent.
- For ALT or AST levels  $> 8x$  ULN, initiate steroid therapy promptly at 1 - 2 mg/kg/day methylprednisolone or oral equivalent
- For all subjects initiating steroids, consult the PI within 24 hours after initiation of steroids. Gastroenterology consult is recommended.
- If AST or ALT levels do not improve within 3- 5 days or the levels worsen after the start of steroid therapy, discuss with the PI the possibility of adding mycophenolate mofetil at 1 g BID.
- Tapering of steroids can start once AST or ALT levels have declined by one CTCAE grade. Taper steroids slowly over no less than 1 month.

As outlined in above, nivolumab and BMS-986205 therapy may resume when AST or ALT have returned to patient's baseline unless the criteria for permanent discontinuation are reached. Subjects who require delay of therapy should be re-evaluated weekly or more frequently if clinically indicated. It is recommended to monitor elevations in AST or ALT approximately every 3-5 days until levels peak or begin to decline. Both therapies can be resumed when re-treatment criteria are met. The PI must be consulted prior to resuming nivolumab for all subjects who required steroid intervention. Tumor assessments for all subjects should continue as per protocol even if study drug dosing is delayed.

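### The laboratory safety summary counts values outside normal limits without baseline or grade, so it will mask part of any hepatic or hematologic worsening in patients who enter abnormal

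*Combined protocol and SAP*

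**What the plan says.** The laboratory part of section 14.4 is half a sentence, repeated in the synopsis under Statistical Considerations: "clinical laboratory values outside normal limits will be listed for each patient and summarized by body system and dose level in frequency tables". The first half of that sentence puts DLTs, adverse events and serious adverse events through the same listing and tabulation. Neither place mentions baseline, CTCAE grade, worst post-baseline value or change.

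The population is described elsewhere:

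- Section 4.1, criteria 10 and 11, allows AST and ALT up to 5 x ULN, total bilirubin up to 2 x ULN, platelets from 50,000/mm3 and hemoglobin from 8 g/dL.
- Section 5.5.3 explains why: "Subjects with advanced HCC generally have underlying cirrhosis with decreased hepatic function". It adds that "Subjects with AST or ALT elevations within the CTCAE Grade 2 range are allowed to enroll in the study", and then sets dose-delay triggers that depend on the patient's baseline category.

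Safety is the phase I primary endpoint and one of the phase II primary endpoints (section 3.0). Section 1.3.1 says that "we have chosen 50 mg QD as the starting dose level to be given with nivolumab 240mg to observe hepatotoxicity in an HCC population". Section 3.0 gives a second reason for the same starting dose: "given the existing safety data for this dose and the safe use of this dose in use with other immunotherapy combinations".

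**The concern.** Counting values outside the normal range works when patients start inside it. Here the protocol deliberately widens entry to people who are already outside it. For such a patient the category is fixed on day 1, and later improvement (short of normalising), stability or marked deterioration all look the same. The count also ignores size: a patient normal at entry who drifts just above the limit counts the same as one who rises many-fold.

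At stake is the readability of a primary-endpoint summary. Liver safety in this population is something the protocol says it wants to observe. The only tabulated laboratory output by dose level would mix cirrhosis present at entry with worsening on treatment.

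**Working it through.** The plan states no figure to reproduce on this point. The check has two parts: what the category can register, and how much worsening the count would show under stated assumptions.

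**1. What the category registers.** Take a patient entering at the AST ceiling of 5 x ULN (section 4.1).

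- At 8 x ULN (8/5 = 1.6-fold), section 5.5.3 calls for a dose delay: for a Grade 2 baseline it uses the lower of 2 x baseline (here 10 x ULN) and 8 x ULN.
- Above 10 x ULN (10/5 = 2-fold) for more than 2 weeks, section 5.6 makes it a hepatic DLT if drug-related.
- Above 15 x ULN (15/5 = 3-fold), section 5.6 makes it a hepatic DLT at any duration if drug-related.

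At all three levels the patient sits in the same outside-normal category as on day 1. Counting values instead of patients does not help: someone abnormal at every visit contributes one value per visit whether stable or worsening.

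**2. How much of the worsening shows.** Inputs:

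- n = 17, the maximum at the MTD, and n = 6, the phase I patients at the MTD (section 14.1).
- b = share abnormal at entry who remain abnormal. The documents give no value; 30% to 90% is assumed.
- h = true rate of worsening on treatment. Assumed 20%, the same whatever the baseline status, and large enough to take a patient with a normal baseline outside the limits.

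Formulas:

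- Expected count without toxicity: n x b
- Expected count with toxicity: n x (b + (1 - b) x h)
- Visible excess: n x (1 - b) x h, against a true n x h
- Share visible: 1 - b, whatever h is
- Chance of at least one newly abnormal patient: 1 - (1 - (1 - b) x h)^n

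Worked line for n = 17, b = 50%: 17 x 0.5 = 8.5 without toxicity; 17 x (0.5 + 0.5 x 0.2) = 10.2 with it; excess 1.7, against a true 17 x 0.2 = 3.4.

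| b (assumed) | Share visible | Excess, n = 17 (true 3.4) | Excess, n = 6 (true 1.2) | P(at least one new), n = 6 |
|---|---|---|---|---|
| 30% | 70% | 2.4 | 0.84 | 0.60 |
| 50% | 50% | 1.7 | 0.60 | 0.47 |
| 70% | 30% | 1.0 | 0.36 | 0.31 |
| 90% | 10% | 0.3 | 0.12 | 0.11 |

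A baseline-referenced table would show all 3.4 or 1.2 expected cases at any b. With n = 6 its chance of showing at least one is 1 - 0.8^6 = 0.74.

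**The case against.** The strongest reply is that section 14.4 does not rely on this table alone. Its sentence begins "DLTs, adverse events, serious adverse events, and clinical laboratory values outside normal limits will be listed for each patient", so hepatic events have other routes into the analysis:

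- The AE definition in section 15.1 covers deterioration of an existing condition and abnormal laboratory findings, and section 5.4 grades AEs by CTCAE v5.0.
- The hepatic DLT limits in section 5.6 lie above the entry ceilings, so baseline abnormality alone cannot reach them.
- Section 15.1.6 requires reporting of any laboratory abnormality that interrupts study drug. The baseline-dependent delays of section 5.5.3 therefore feed into reporting.
- Section 15.1.8 makes potential drug-induced liver injury an SAE.
- In a trial of about 23 patients, a listing of out-of-range values can be read by eye.

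This stands, and it rules out the reading that the plan cannot show hepatotoxicity or has no other laboratory output. It does not close the gap. Hepatic DLTs need high thresholds, drug attribution and an early window (6 weeks in section 5.6, 56 days in section 3.0). The liver-injury definition drops cases with another apparent cause, expressly including chronic liver disease. Other laboratory AEs depend on judgement of significance or on action taken, and section 14.4 does not promise AE tables by grade. Listings are not a summary by dose level.

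It is also fair that entry limits are ceilings, not distributions. Child-Pugh A (section 4.1, Appendix 6) holds the score to 6, so bilirubin of 2 to 3 mg/dL, at 2 points, leaves no room for another abnormal component. That restrains bilirubin, but AST, ALT, platelets and hemoglobin are not in the score.

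Finally, section 14.4 does not say how the frequency table is built, and it does not exclude grading. The calculation above therefore rests on reading it as a count of patients.

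**Conclusion.** The point holds as a limitation of one summary. As written, the laboratory frequency table has no baseline reference and no grade, and it will mask part of any hepatic or hematologic worsening among patients abnormal at entry. The masked share equals the share abnormal at entry who stay so: 30% to 90% masked across the assumed range, and complete only if every patient enters abnormal. That range is an assumption, as are the 20% worsening rate and its independence from baseline.

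Three stronger inferences are not supported:

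- Hepatotoxicity is not the sole rationale for starting at 50 mg; it is one of two stated reasons.
- The baseline argument does not extend to methemoglobin, because exclusion criterion 13 screens for levels above ULN.
- No formal comparison of 50 mg with 100 mg is planned. Escalation rests on DLT counts in 3 to 6 patients, so this table drives no stated decision, and no table would make such small groups comparable.

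No sample size, error rate or decision threshold is affected. The change is still worth making, because safety is a primary endpoint and section 5.5.3 already accepts the baseline-relative principle.

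**What to change.** In section 14.4 and the matching synopsis text, add by dose level:

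- (a) shift tables of baseline CTCAE v5.0 grade by worst on-treatment grade for AST, ALT, total bilirubin, hemoglobin and platelets;
- (b) each patient's maximum AST, ALT and total bilirubin, as a multiple of that patient's own baseline and of ULN.

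Define baseline, and use the same grading reference at both time points of the shift table. Name CTCAE v5.0 explicitly, because the general severity scale in section 15.1.1 words Grades 2 and 3 identically. Keep the existing listings and the DLT, AE, SAE and out-of-range tables.

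The cost is a little programming. The study calendar in section 10.0 already collects blood counts and biochemistry at screening and on day 1 of each cycle, so no visit, test or patient is added and no clinical rule changes.
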